2.2. Provide the name of the Coordinating Center. Yes  No  N/A  CMCVAMC

2.3. List the name of the other sites involved. **VA Pittsburgh; University of Pennsylvania**

2.4. Provide the FWA numbers for each of the other sites involved. 00001282 (VA Pittsburgh); 00004028 (Penn)

**THE FOLLOWING INFORMATION MUST BE CMCVAMC-SPECIFIC, THAT IS, SPECIFIC TO WHAT WILL BE DONE WITH CMCVAMC-RECRUITED VETERANS.**

**H. Background and Significance:** (Describe succinctly and clearly the past findings which justify the plan for this project. A summary of the relevant literature in the area of interest and reports of previous studies should be included.)

1. **Opioid Use in the Treatment of Pain**

The prevalence of chronic pain continues to increase in the United States causing individual suffering and contributing to morbidity, mortality and disability. It has been estimated that over 100 million Americans suffer from chronic pain. In the Veteran population, improvements in battlefield medicine have resulted in large numbers of Veterans of Iraq and Afghanistan surviving injuries that in previous wars would have resulted in fatalities. A substantial percentage of these Veterans experience clinically significant pain and many require treatment with opioid analgesics. Clark et al. randomly selected and reviewed 300 charts of U.S. Veterans from a general medical population. They found that 50% of patients suffered from chronic pain and approximately 75% of the patients with chronic pain were prescribed at least one analgesic. Although non-steroidal anti-inflammatory drugs were the most commonly prescribed class of analgesics, 44% of patients receiving an analgesic received opioids. Wu et al. have also reported a rise in the prevalence of opioid use in young Veterans. Within the VA, chronic pain management and thus opioid prescriptions are almost exclusively provided within the primary care program.

2. **Risky Alcohol Use in Returning Service Personnel and Veterans**

Alcohol misuse is the fourth leading cause of disability worldwide and is associated with increased mortality. Alcohol is, after nicotine, the most frequently abused substance among Veterans. The Veterans Health Study found that 12.1% of outpatients

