- 2.2. Describe how randomization or other treatment assignment will be made. **Veterans who meet criteria for participation will be randomly assigned to one of the two treatment conditions. Urn randomization will be used to balance the groups on three factors: gender, benzodiazepine or other drug use, and age. We will also be blocking on whether the person admits use or not when we do the randomization, so we get equal numbers of non-users in each condition. Urn randomization is a kind of biased-coin randomization where probability of being assigned to a group decreases if the group is overrepresented and increases if the group is underrepresented. As the sample size increases, the randomization shifts from perfect balance to complete randomization.**
- 2.3. For retrospective research studies, provide the "look-back" period. (e.g., December 1, 1999 through December 31, 2008.) **n/a**

3. **Study Duration**

- 3.1. Provide the estimated length of time to enroll all subjects and complete the study. **2.5 years of enrollment, but 5 years total for study start up, enrollment, completion, and analyses.**
- 3.2. Explain the expected duration of subject participation including any follow-up. **18 months for patients enrolled prior to 4/1/2019; 12 months for patients enrolled after 4/1/2019**
- 3.3. Specify the projected date of completion of the proposed study. **5 years from date of funding.**

4. **Drug Information** (If not applicable state, "Not Applicable.") **Not Applicable**

- 4.1. Specify if the drug or biological agent is:
  - 4.1.1. FDA approved
  - 4.1.2. Used for off-label purposes
  - 4.1.3. Not yet FDA approved.
- 4.2. Include the FDA Investigational New Drug (IND) number for all non-FDA approved and off-label drugs, biological agents or nutritional supplements. If not applicable state, "Not Applicable."
- 4.3. Provide all relevant information about the drug
- 4.4. Explain any wash-out periods, rescue medications permitted and any type of medications not permitted while enrolled in the study.
- 4.5. Describe blinding and un-blinding procedures.

- 4.6. Include the dosage, route of administration, previous use, and the safety and efficacy information on any drug used for research purposes.
- 4.7. Describe rationale for the dosage in this study.
- 4.8. Justify why the risks are reasonable in relation to anticipated benefits and/or knowledge.
- 4.9. Describe where drug preparation will be done.

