#### **Study visits:**

In addition to the intervention, all participants will be seen at 3, 6, 9, 12, and 18 months post baseline for research follow ups. Participants enrolled after 4/1/2019 will only be seen at 3, 6, 9, and 12 months post baseline for research follow ups. These will be done at the CMCVAMC and will take approximately 1.5 hours. The schedule of assessments (all of which are for research purposes only and not part of standard care) is as follows: SCID and MINI (B); Blood samples (%dCDT and GGT) (B and 18m); Time Line Follow-Back, SIP (B, 3, 6, 9, 12, 18); Drug urine toxicology tests (B, 3, 6, 9, 12, 18); Self-efficacy, Coping, Social Support, Readiness to Change, pain, depression, quality of life (B, 3, 6, 9, 12, 18).

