**CMCVAMC: 42**  
**Pittsburgh VA: 3**  
**University of Pennsylvania: 6**

- 1.1 Explain if and how the follow-up of subjects will occur. **Research follow up visits will occur at 3, 6, 9, 12, and 18 months post baseline. For participants enrolled after 4/1/2019 research follow up visits will occur at 3, 6, 9, and 12 months post baseline. Participants will complete a locator form at baseline to assist the study team in scheduling future research visits. Subjects can fill out as much or as little of this form as they want to.**
- 1.2 Describe where, how and who will be conducting study procedures. **Research staff will administer the questionnaires, interviews, and collect urine samples from participants. CMCVAMC lab staff will collect blood.**
- 1.4 If a survey study, specify the estimated amount of time that subjects will need to complete the questionnaires/tools. **Baseline assessments will take approximately 2.5 hours and follow up visits will take approximately 1.5 hours.**
- 1.5 If a blood draw, specify the amount of blood to be drawn in milliliters and in teaspoons or tablespoons and specify how often and where the blood will be drawn. **Blood will be drawn in the CMCVAMC lab on the third floor by CMCVAMC lab staff. Two tubes of blood (4 teaspoons or 20 mL) will be collected, one tube (2 teaspoons) for disialo carbohydrate-deficient transferrin (%dCDT) testing and the other (2 teaspoons) for gamma-glutamyl transferase (GGT) testing. The CMCVAMC lab will conduct the GGT testing. The second tube of blood will be centrifuged and have the serum extracted by the TRC (Treatment Research Center) at the University of Pennsylvania who will then prepare the serum for shipping to the MUSC for the %dCDT testing.**

2. **Data Collection** (Include all questionnaires and survey tools with the submission.)
  - 2.1. Provide
    - 2.1.1. the mode of data collection, e.g. telephone, in-person, questionnaire, interviews, **Data will be collected via paper and stored in locked cabinets in MIRECC., and by direct data entry into the intranet web-based system housed on the CMCVAMC server. It will be set up on the CMCVAMC server (<https://vhaphimulh12.v04.med.va.gov/dmumain/>), and accessed through the CMCVAMC intranet)**

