#### R. Subject Recruitment (characteristics of the study population)

1. Provide the planned or targeted enrollment at:
  - 1.1. CMCVAMC - 115 (90 undergoing treatment and 25 just being followed and not undergoing one of the treatment groups)
  - 1.2. Other sites - 60 (10 at VA Pittsburgh; 50 at Penn)
  - 1.3. Not applicable; chart review or use of previously collected data -

2. **Screening and/or Eligibility Requirements - Inclusion/exclusion criteria are the same for screening before and after consent, however, some assessments used to determine final eligibility (such as the SCID and the MINI) are only administered once the Veteran comes to the lab (which occurs after a positive phone screen)**

2.1. Describe and provide justification for:

2.1.1. Inclusion criteria: **To be eligible for participation, Veterans must: (1) currently be receiving daily treatment with a prescription opioid for chronic pain, OR receive a daily prescription for opiate replacement therapy and have a chronic pain diagnosis; (2) be between the ages of 18 and 75; (3) have a cell phone capable of receiving text messages; (4) and be willing to be in a study where they might receive text messages.**

**If at some point during follow-up research visit, if a subject admits to drinking they will move on to the treatment arm that they were randomized to upon entry into the study.**

2.1.2. Exclusion criteria: **Veterans will not be eligible if they: (1) meet DSM-V criteria for a moderate to severe alcohol or drug disorder (with the exception of nicotine abuse/dependence); (2) have a current psychotic disorder severe enough to require inpatient treatment; or (3) are participating in alcohol use treatment at the VA or elsewhere (with exception of screening and brief intervention at the VA); (4) are currently on palliative care or are being treated with opioids for cancer-related pain.**

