11. **Waiver or Alteration of Informed Consent Requirements/Waiver of Requirement to Obtain Documentation of Informed Consent**

- 11.1. Are you requesting a waiver or alteration of informed consent? *(Check all that apply)*
  - 11.1.1. No
  - 11.1.2. Yes; provide justification.
  - 11.1.3. Yes; for recruitment purposes only.
- 11.2. **Are you requesting a waiver to obtain documentation of informed consent?**
  - 11.2.1. No
  - 11.2.2. Yes; provide justification.

S. **Compensation** (*The amount of compensation may not constitute an undue inducement to participate in the research.*)

1. Summarize any financial compensation that will be offered to subjects. **Veterans that complete the baseline assessment prior to 4/1/2019 will be compensated \$75, then \$50 for each follow up research visit completed. Veterans that complete the baseline assessment after 4/1/2019 will be compensated \$75 for the baseline visit, then \$50 for the follow up research visits at 3, 6, and 9 months, then \$75 for the final 12 month research follow up visit.**

2. Provide the schedule for compensation. **Veterans that complete the baseline assessment will be compensated \$75, then \$50 for each follow up research visit completed (3 month, 6 month, 9 month, 12 month, and 18 month). Veterans who are enrolled after 4/1/2019 will be compensated \$75 for the baseline visit, then \$50 for the follow up research visits at 3, 6, and 9 months, then \$75 for the final 12 month research follow up visit.**
  - 2.1. Per study visit or session. **\$50 to \$75 as described.**
  - 2.2. Total amount for entire participation. **\$325 for participants enrolled prior to 4/1/2019; \$300 for participants enrolled after 4/1/2019**

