#### **U. Risk/Benefit Assessment**

1. **Potential Study Risks**
  - 1.1. Describe and assess all of the following risks that may be associated with the research:
    - 1.1.1. **Physical There is a small chance of mild pain and swelling where the needle enters the skin and vein, bruising, infection and possibly fainting during the blood draws at baseline and 18 months. Texting (reading and sending) while driving may potentially lead to automobile accidents and bodily injury.**
    - 1.1.2. **Psychological There is a small chance that talking about their personal history can be embarrassing and/or lead to psychological discomfort.**
    - 1.1.3. **Social There is slight risk of embarrassment in terms of coming to the MIRECC suite for the research as MIRECC is geared towards research with mental illness and the stigma associated with mental illness.**

- 1.1.4. Economic **There is no foreseeable economic risk to participation.**
- 1.1.5. Monetary **The Veteran will not have to pay for treatment or participation but will need to pay for transportation to get to the research visits.**
- 1.1.6. Legal **There is no foreseeable legal risk associated with the research. In Pennsylvania it is illegal to text while driving.**
- 1.1.7. Loss of confidentiality **In all research, indeed in all situations, there is a risk of a loss of confidentiality. For instance, if the participant does not have a password on their phone, anyone could pick up their phone and be able to read their confidential messages. This is of incredible importance to the research team and confidentiality will be closely guarded. We will guard participants' information through secure servers (for web-based data) and in locked cabinets in with the MIRECC suite (for paper-based data). In addition, there is the risk that a person authorized to access the text messages might use them for an unauthorized purpose or disclose them to an unauthorized party.**
- 1.1.8. Assess the likelihood and seriousness of such risks. **Low.**
- 1.1.9. Other **N/A**

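### At CMCVAMC the only post-baseline %dCDT/GGT draw is at month 18, but participants enrolled after 4/1/2019 finish at month 12 and so, as written, have no follow-up biomarker value

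*Combined protocol and SAP*

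**What the plan says.** **Blood draws.** Section O.1 (Study visits) schedules "Blood samples (%dCDT and GGT) (B and 18m"; no other time is given. Section U.1.1.1 describes the risk of "possibly fainting during the blood draws at baseline and 18 months". Item 1.5 of section O, on the blood draw, gives volume, tubes and place but no timing.

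**Length of follow-up.** The Study visits paragraph also says: "Participants enrolled after 4/1/2019 will only be seen at 3, 6, 9, and 12 months post baseline for research follow ups". M.3.2 gives the duration of participation as "18 months for patients enrolled prior to 4/1/2019; 12 months for patients enrolled after 4/1/2019". O.1.1 repeats: "For participants enrolled after 4/1/2019 research follow up visits will occur at 3, 6, 9, and 12 months post baseline". Section S pays late enrollees $75 "for the final 12 month research follow up visit".

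**Role and analysis.** GGT and CDT appear in J.2, secondary Hypothesis 1, and in the secondary outcomes of sections L and W.1. W.4.2.b compares the groups on them with mixed effects linear models after transformation. No section moves the second draw, adds another, or restricts the biomarker analysis to earlier enrollees.

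**Scope.** The form states that its content must be "SPECIFIC TO WHAT WILL BE DONE WITH CMCVAMC-RECRUITED VETERANS". Planned enrolment in R.1 is "CMCVAMC - 115 (90 undergoing treatment and 25 just being followed and not undergoing one of the treatment groups").

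**The concern.** When follow-up was shortened for late enrollees, the blood schedule was not changed with it. Staff who follow the schedule literally would take a baseline sample from this cohort and never a second. Their baseline values alone tell us nothing about change after the intervention, and a sample not taken at the last visit cannot be obtained later.

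The biomarkers matter more here than their secondary status suggests. Risky drinking and heavy drinking days both come from the Timeline Follow-Back interview. Urine toxicology addresses other drugs, and overdose records are not a measure of drinking. That leaves %dCDT and GGT as the only alcohol outcomes independent of what the Veteran reports. The March 2018 amendment text in section O.1 says the sponsor suspects under-reporting of alcohol among Veterans who fear losing their opioid prescription, and it opened enrolment to those who deny drinking. Everyone enrolled after 4/1/2019 entered under that rule, so an objective follow-up measure is missing where the sponsor's own reasoning makes it most useful.

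**Working it through.** The plan gives no sample size, power or precision figure for the biomarkers, so there is none to reproduce. The check compares schedules and then bounds the number affected.

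**1. Scheduled draws against scheduled visits** (Study visits, U.1.1.1, M.3.2, O.1.1). Draws are at {B, 18}.

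| Enrolled | Visits | Draws that fall on a visit | Post-baseline values |
|---|---|---|---|
| Before 4/1/2019 | B, 3, 6, 9, 12, 18 | B, 18 | 1 |
| After 4/1/2019 | B, 3, 6, 9, 12 | B | 0 |

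**2. Is month 12 really the last visit?** The payment totals in section S give an independent check.
- Before 4/1/2019: 75 + 5 × 50 = $325, which matches the stated total and implies five follow-up visits.
- After 4/1/2019: 75 + 3 × 50 + 75 = $300, which matches the stated total and implies four follow-up visits ending at month 12.

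**3. Do other measures share the problem?** The Timeline Follow-Back, SIP, urine toxicology and the questionnaires are listed at B, 3, 6, 9, 12 and 18. For late enrollees the overlap with their visits is B, 3, 6, 9 and 12, so each keeps four post-baseline values. The SCID and MINI are baseline-only by design. Blood is the only repeated measure that loses its sole follow-up point.

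**4. How many could be affected at CMCVAMC?** Inputs: 115 planned (R.1) and 42 randomised there by the March 2018 amendment (section O.1).
- Upper bound: 115 − 42 = 73, or 73/115 = 63%. This requires that nobody enrolled at CMCVAMC between the March 2018 count and 4/1/2019.
- Lower bound: 0, if CMCVAMC enrolment ended before 4/1/2019.

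The documents give no count nearer to 4/1/2019, so the range cannot be narrowed.

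**The case against.** The strongest reply is that this is a list nobody updated. Every repeated measure in the Study visits paragraph still ends at 18, although late enrollees have no such visit, so 18m may simply have meant the last visit. The larger month-12 payment could hint that end-of-study procedures moved there. This is plausible, but no section says it, and U.1.1.1 repeats month 18 without qualification. For the other measures the stale entry is harmless; for blood it removes the only follow-up value.

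A second reply is that a value absent solely because of enrolment date is missing by design, and that W.4.2.e already relies on ignorable missingness. That stands as far as validity goes. It does not restore the values, and the pattern-mixture analysis described there is for primary outcomes.

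A third is that the bound of 73 is wide and may include Veterans who are only followed. That also stands. R.1 counts 25 such participants within the 115. Non-drinkers were admitted only from March 2018, so if all 42 already randomised count toward the 90 treated, the bound among treated participants is 90 − 42 = 48 of 90. The true number may be zero.

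Finally, the matter concerns one secondary outcome, and the repair is a scheduling change. That is fair, and it limits the severity.

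**Conclusion.** The inconsistency is certain on the text: at CMCVAMC, participants enrolled after 4/1/2019 have no scheduled post-baseline %dCDT or GGT. The number affected is between 0 and 73 of 115, assuming the R.1 target is met and not exceeded. The importance is minor to moderate.

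Four stronger readings are tempting and are not supported.
- **A stated loss of precision or power.** A reader might infer one. The late share is not given, and the plan states no power for the biomarkers, so any such figure would rest on invented inputs.
- **A count for all sites.** The form covers CMCVAMC only, and blood timing at Penn and Pittsburgh is not described. The all-site totals also disagree: 200 in the March 2018 amendment text against 115 + 60 = 175 in R.1.
- **Bias between arms.** The gap is set by enrolment date, and both arms are randomised on either side of it, so no imbalance by arm is expected.
- **Damage to the primary outcome.** Risky drinking comes from the Timeline Follow-Back, which late enrollees still complete at months 3 to 12. The missing blood draw does not affect it.

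**What to change.** In O.1 (Study visits) and U.1.1.1, set the second research draw at the participant's final scheduled visit: month 18, or month 12 for the cohort whose follow-up ends there. If the consent form states draw times, it should agree.

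Keep the mixed effects linear model of W.4.2.b and enter visit month as a time term, so that month-12 and month-18 values are not treated as one time point. The plan already allows group-by-time terms where appropriate. Month 12 against month 18 will coincide with enrolment cohort, so a difference between the two should not be read as a pure time effect.

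The cost is a short amendment and one extra research draw and assay per late enrollee, at a visit that already takes place. The limitation is that a month-12 value reflects the end of the 12-month intervention. It cannot show the 18-month persistence described in U.2.1.

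If the omission was intended, one sentence in the Study visits paragraph and one in W.4.2.b should say that the biomarker comparison is limited to participants enrolled before 4/1/2019. That costs almost nothing and makes the plan consistent, but it leaves the late cohort without an objective follow-up measure of alcohol use.

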#### **October 2015 Amendment**

Because of the potential subjects were concerned about the “integrated” aspect of the study and how it might influence their clinical care, we submitted an amendment to remove the integration of the study and leaving research notes summarizing their status will no longer be the default. We have contacted the DoD about this change, and they are fine with it. The “integrated” nature was not an important piece. At a yearly progress meeting for DoD grant recipients, most of the other SUD related project have made it a point to NOT integrate their interventions with veterans’s medical care, as it sharply reduces recruitment rates.

We have randomized 7 subjects. We will notify them of the change, and re-consent them.

**January 2016 Amendment** - An amendment to the protocol has been made adding two sites to the study, with the CMCVAMC being the coordinating site. We are adding VA Pittsburgh as well as recruiting veterans not seen by the CMCVAMC at the University of Pennsylvania site. These sites are being opened up to address the poor recruitment numbers at the CMCVAMC site.

There is also a change to where the data is housed. Now instead of data being housed on a secure server in the VA, it is housed on a secure server at the University of Pennsylvania. An Off-Site Storage form is included. Additionally, the Penn/PVAMC MOU is included.

Paper based data will ultimately be kept at the CMCVAMC. However, electronic data will be combined and stored at Penn. The direct data entry can be done at Pittsburgh, CMCVAMC, and Penn, as long as there is internet access.

**July 2016 Amendment** – An amendment to the protocol has been made to change the server back to the secure server at the VA. The reason for this is an issue with software and being able to get through the VA firewall for data entry.

Paper based data will ultimately be kept at the CMCVAMC. Electronic data for Pittsburgh and CMCVAMC will also be stored at the CMCVAMC. Penn data will be stored at Penn as there is no way to access the VA server from outside the VA.

**January 2017 Amendment** - Previously Veterans had to score a four or greater (females 3 or greater) on the AUDC during the initial phone screen to be eligible to participate in the study. We have lowered this threshold to a score of two, as this score can still be indicative of regular/heavy alcohol use that would place Veterans prescribed chronic opiates at risk.

According the NIAAA, any alcohol use with contraindicated medications (like opiates) is considered risky:

*Certain people should avoid alcohol completely, including those who:*

- *Plan to drive a vehicle or operate machinery*
- *Take medications that interact with alcohol*
- *Have a medical condition that alcohol can aggravate*
- *Are pregnant or trying to become pregnant*

[\(https://www.niaaa.nih.gov/alcohol-health/overview-alcohol-consumption/moderate-binge-drinking\)](https://www.niaaa.nih.gov/alcohol-health/overview-alcohol-consumption/moderate-binge-drinking)

Risky drinking will be ascertained during the AUDIT-C. Usually when administering the AUDIT-C, individuals will give vague answers (i.e. “every now and then”) that require follow up questions. For instance, if a Veteran affirms a period of time when they drank 6+ drinks in the past year, the interviewer could ask, “When was the last time that happened?” When asking about consumption the interviewer will be able to ascertain if the Veteran’s level of consumption meets this threshold (questions two and three) either with the Veteran’s initial response or with follow up questions.

We have also included language on how this will affect standard care through the BHL. As Veterans will be referred with lower levels of alcohol use (but still risky), after BHL triage it is possible that these Veterans will not receive a brief intervention.

Further, our business office is moving away from using petty cash to compensate research participants. Instead, we are switching to the Greenphire ClinCard system. ClinCard functions like a Visa debit card, and money can be loaded on to the card remotely by study staff. Our protocol has been updated to describe the system, how it functions, how Veterans will be paid.

**March 2018 Amendment**- We are changing the name of the study to something that sounds less threatening to Veterans who may fear losing their opiate prescription if they admit to drinking alcohol. We plan to change it to "Assisting Veterans in the Safe Use of Prescription Opioids."

Further, we plan to change the inclusion criteria to include Veterans on prescription opiates for chronic pain regardless of whether or not they admit to drinking alcohol.

As part of broadening the inclusion criteria we plan to add a third group to the adaptive intervention. We will enroll and randomize the Veterans who do not admit to drinking and place them in a monitoring category where we continue to assess them and if they admit to consuming any amount of alcohol we would then transfer them to the treatment arm into which they had been randomized. This change is a significant change to the study but does not change the aims or outcomes and it does not increase the risk. It is a change supported by the DOD as a way to increase enrollment and reach veterans that we think may be less truthful about their alcohol use out of fear that they will have their opiate prescriptions taken away.

Following up those who initially deny drinking will provide important data for the VA. The yearly AUDIT screening appears to be underestimating the numbers of vets who are drinking alcohol. If our data indicate that a significant percentage of those who deny drinking at the start of the study end up reporting drinking later in the follow-up, it will be in indication that at risk patients (i.e., those on opioid meds) are at risk due to underreporting of their drinking, which could be an unintended consequence of the current VA policies.

We also will no longer be using the AUDIT-C.

Additionally, we have decreased the total n for the study to 150 from all sites. That is, 200 subjects from all sites being randomized (with 150 participants drinking and entering TX phase and 50 participants not drinking (25 at CMCVAMC and 25 at Penn).

Moreover, there is a personnel change. [name] is no longer a Research Coordinator on this study.

Lastly, SenseHealth has changed its name to Wellpass and the TRC has moved its location to [name]

At the time of this amendment, the following number of subjects have been randomized at the following sites:

